Appendix 5. Sampling Summary

This table summarizes the approximate number of samples and volumes for all sampling and tests during the study. Fewer samples may actually be taken, but this will not require a protocol amendment.

Protocol GLWL-PWS Sampling Summary

Purpose	Sample Type	Maximum Amount per Sample	Maximum Number of Samples	Maximum Total Amount
Screening tests ^a	Blood	21 mL	1	21 mL
Standard laboratory tests ^a	Blood	2 mL	5	10 mL
Drug concentration	Blood	2 mL	14	28 mL
AG and UAG samples	Blood	4 mL	5	20 mL
On-study serum chemistry (includes serum thyroid-stimulating hormone, lipid panel, troponin , and serum pregnancy when done at the same time)	Blood	15 mL	5	75.0 mL
Total	Blood	-	-	154.0 mL
Hepatic monitoring ^b	Blood	3 - 30 mL	-	-

^a Additional samples may be drawn if needed for safety purposes.

^b Based on laboratory safety values, unscheduled hepatic monitoring testing may be performed as part of patient follow-up, in consultation with Lilly-designated Medical Monitor.

**Appendix 8. Protocol Amendment GLWL-PWS(c)
Summary [A Phase 2 Study to Evaluate Efficacy, Safety,
and Pharmacokinetics of GLWL-01 in the Treatment of
Patients with Prader-Willi Syndrome]**

Overview

Protocol GLWL-PWS [A Phase 2 Study to Evaluate Efficacy, Safety, and Pharmacokinetics of GLWL-01 in the Treatment of Patients with Prader-Willi Syndrome] has been amended. The new protocol is indicated by amendment (c) and will be used to conduct the study in place of any preceding version of the protocol.

The overall changes and rationale for the changes made to this protocol are as follows:

- Troponin has been listed separately in the Schedule of Activities for clarification purposes; no changes have been made to laboratory draws
- Exclusion Criterion #23c flexibility added. The previous language explicitly prohibited enrolling patients on “any medications that prolong the QT/QTc interval.”
 - The original request for adding the QTc prolonging medications to the exclusion criteria came from HC (Control #208160, CR File Number: HC6-24-c208160); and prompted amendment (a). However, the suggested wording from Health Canada stated the medications could be used “with caution,” which was not accurately reflected in the amended protocol.
 - In addition, the criterion was prior to availability of QT/QTc data. We currently have data from 9 enrolled Prader-Willi patients that have completed between 5 and 9 visits in this study, in addition to 38 diabetes patients that received GLWL in a previous study (GLWL-SMP).
 - There has been no QT/QTc prolongation observed to date.
 1. In addition to regular ECGs to assess intervals, we are measuring troponins
 2. Prolongation of the QT/QTc interval >500 ms or >60 ms over baseline, judged medically significant following repeat ECG after 5 minutes of rest from the initial ECG remains a discontinuation criterion.
 - At this time, we feel there is enough evidence to proceed with the new wording for Exclusion Criteria #23c of, “Any medications that prolong the QT/QTc interval will be excluded, unless the patient has been stable on the medication for at least 3 months and has a QTc <450 msec at Visit 1 and Visit 3.”

- Section 7.7 Concomitant Therapy verbiage has been updated to allow inclusion of patients on stable doses of medications that have been publicly noted to potentially cause QTc prolongation.

Revised Protocol Sections

Note: Deletions have been identified by ~~strikethroughs~~ or grayed out for figures.
Additions have been identified by the use of underscore.

Table GLWL-PWS.4. Schedule of Activities

Period	Screening ^a	Treatment Period 1			Washout (28 days)	Treatment Period 2			Follow-up	ET ^c		
Phase		Single-blind Placebo Lead-in Phase (14 days)	Double-blind Treatment Phase (28 days) ^b				Single-blind Placebo Lead-in (14 days)	Double-blind Treatment Phase (28 days) ^b				
Visit No/ Type Procedure	V1	V2 ^c Phone	V3 ^d	V4	V5	V6 ^e Phone	V7 ^e Phone	V8	V9	V10	V11	
Day	-28 to -3	0 (±3)	14 (±2)	21 (±2)	42 (±2)	56 (±2)	70 (±2)	84 (±2)	91 (±2)	112 (±2)	126 (±3)	
12-lead ECG 2 hours post-dose ^k			X					X				
Serum pregnancy test ^l	X									X		X
Urine pregnancy test ^l			X					X				
Clinical chemistry and hematology ^h	X		X	X	X			X	X	X		X
Troponin			X	X	X			X	X	X		
Lipid panel			X		X			X		X		X
AG and UAG ^m			X		X			X		X		X
Plasma sample collection for PK analysis ⁿ			X		X							X
C-SSRS	X	X	X	X	X	X	X	X	X	X	X	X
Adverse events	X	X	X	X	X	X	X	X	X	X	X	X

6.2 Exclusion Criteria

23. Unable to refrain from or anticipates the use of

- a. Any drugs known to be significant inhibitors of cytochrome P450 (CYP)3A enzymes and/or P-glycoprotein (P-gp) including regular consumption of grapefruit or grapefruit juice for 14 days prior to the first dose of study medication and throughout the study. Appropriate sources will be consulted by the principal investigator (PI) or designee to confirm lack of PK or pharmacodynamic (PD) interaction with study medication. Acetaminophen (up to 2 g per 24-hour period) may be permitted during the study.
- b. Any drugs known to be significant inducers of CYP3A enzymes and/or P-gp, including St. John's Wort, for 28 days prior to the first dose of study medication and throughout the study. Appropriate sources will be consulted by the PI or designee to confirm lack of PK/PD interaction with study medication.
- c. Any medications that prolong the QT/QTc interval, unless the patient has been on a stable dose of said medication for at least 3 months and has a QTc <450 msec at Visit 1 and Visit 3.

7.7 Concomitant Therapy

Patients may not take any medication (including over-the-counter products), herbal products, or vitamin supplements, which are CYP3A and/or P-gp inhibitors for 14 days prior to dosing and throughout the study. In cases that require the use of such medication for the treatment of an AE or comorbidity, GLWL-01 dosing must be terminated before the CYP3A inhibitor can be started.

Medications that prolong the QT/QTc interval are prohibited acceptable, per the investigator's judgement. A list of medications with a potential for QTc prolongation will be provided separately and updated as data evolves to the investigators.

If the need for the initiation of other medication arises during the study, the investigator must consult with sponsor medical representative and such medication change must be reported in the EDC.

All medications taken by patients during the course of the study will be recorded. Concomitant medications will be listed by treatment and coded using the most current World Health Organization drug dictionary.

**Appendix 9. Protocol Amendment GLWL-PWS(d)
Summary [A Phase 2 Study to Evaluate Efficacy, Safety,
and Pharmacokinetics of GLWL-01 in the Treatment of
Patients with Prader-Willi Syndrome]**

Overview

Protocol GLWL-PWS [A Phase 2 Study to Evaluate Efficacy, Safety, and Pharmacokinetics of GLWL-01 in the Treatment of Patients with Prader-Willi Syndrome] has been amended. The new protocol is indicated by amendment (d) and will be used to conduct the study in place of any preceding version of the protocol.

The overall changes and rationale for the changes made to this protocol are as follows:

- Language regarding QTc prolongation medications in Section 7.7, Concomitant Therapy, has been clarified at the request of Health Canada.

Revised Protocol Sections

Note: Deletions have been identified by ~~strikethroughs~~ or grayed out for figures.
Additions have been identified by the use of underscore.

7.7 Concomitant Therapy

Patients may not take any medication (including over-the-counter products), herbal products, or vitamin supplements, which are CYP3A and/or P-gp inhibitors for 14 days prior to dosing and throughout the study. In cases that require the use of such medication for the treatment of an AE or comorbidity, GLWL-01 dosing must be terminated before the CYP3A inhibitor can be started.

Medications that prolong the QT/QTc interval are allowed provided the patient has been on a stable dose of said medication for at least 3 months and has a QTc < 450 msec at Visit 1 and Visit 3, acceptable, per the investigator's judgement. A list of medications with a potential for QTc prolongation will be provided separately to the investigators.

If the need for the initiation of other medication arises during the study, the investigator must consult with sponsor medical representative and such medication change must be reported in the EDC.

All medications taken by patients during the course of the study will be recorded. Concomitant medications will be listed by treatment and coded using the most current World Health Organization drug dictionary.

**ABBREVIATIONS/DEFINITIONS**

Abbreviation	Definition
AG	acylated-ghrelin (AG)
AE	adverse event
AUC 0-12	Area under the concentration versus time curve from time zero to 12 hours
BMI	body mass index
CGIC	Caregiver Global Impression of Change
CSR	clinical study report
C-SSRS	Columbia-Suicide Severity Rating Scale
eCRF	electronic case report form
GOAT	ghrelin-O-acyltransferase
HQ-CT	Hyperphagia Questionnaire for Clinical Trials
IRT	Interactive response technology
MedDRA™	Medical Dictionary for Regulatory Activities
MMRM	Mixed effects model repeated measures
PK	pharmacokinetic
PWS	Prader-Willi Syndrome
QT	time between the start of the Q wave and the end of the T wave in the heart's electrical cycle
QTc F	QT interval corrected for heart rate using Fridericia's formula
SAE	serious adverse event
SAP	Statistical analysis plan
SOC	system organ class
TEAE	treatment emergent adverse event
UAG	unacylated-ghrelin
WHODD	World Health Organization Drug Dictionary

## **1. INTRODUCTION AND OBJECTIVES**

### **1.1. Introduction**

The purpose of this statistical analysis plan (SAP) is to describe the analysis variables and statistical procedures that will be used to analyze and report the results from a Phase 2 study evaluating the safety and efficacy of GLWL-01, an inhibitor of the ghrelin-O-acyltransferase (GOAT) enzyme that converts UAG into AG, in patients with Prader-Willi Syndrome (PWS). This SAP is based on the amended protocol, Protocol GLWL-PWS(d), which was approved on 27 June 2018.

Changes to the protocol that impact the design, the data collected, or the statistical methods and that occur after the finalization of this SAP may require an amendment to the approved SAP. Similarly, changes to the planned analysis variables or statistical methods described in the approved SAP may also require an amendment to the SAP.

The formats for the tables, listings, and figures described in this SAP are provided in a companion document. Changes to the formats of these reports that are decided after the finalization of the SAP will not require an amendment. In addition, any additional supportive or exploratory analyses requested after SAP approval will not require amendment of the SAP. These additional analyses will be described in the clinical study report (CSR).

Please see the study protocol for details about the study design, procedures, and schedule of assessments and see the electronic case report form (eCRF) for details about variables collected and their possible values.

### **1.2. Study Objectives**

Table 1 shows the objectives and endpoints of the study.

**Table 1. Objectives and Endpoints**

Objectives	Endpoints
Primary 

• Evaluate the efficacy of GLWL-01 compared with placebo in reducing hyperphagia-related behaviors after 28 days of treatment in patients with PWS as measured using the Hyperphagia Questionnaire for Clinical Trials (HQ-CT)

	

• Post-treatment HQ-CT total score

Secondary 

• Evaluate the safety and tolerability of GLWL-01 after 28 days of treatment in patients with PWS

	

• Treatment-emergent adverse events

Objectives	Endpoints

 
Evaluate the efficacy of GLWL-01 compared with placebo in reducing hyperphagia-related behaviors after 28 days of treatment in patients with PWS as measured using the Caregiver Global Impression of Change (CGIC)
 
Evaluate the pharmacokinetics after single and multiple oral dosing of GLWL-01 in patients with PWS
 
	
 
CGIC score
 
GLWL-01 
 
Area under the concentration versus time curve from time 0 to 12 hours (AUC0-12)
 
Maximum observed drug concentration (Cmax)
 
 
 

Exploratory 
 
Evaluate the effect of GLWL-01 in the following measures in patients with PWS 
 
Acylated-ghrelin (AG)
 
Unacylated-ghrelin (UAG)
 
AG/UAG ratio
 
Body weight
 
Percentage fat mass
 
Body mass index
 
Waist circumference
 
Low-density lipoproteins
 
Total cholesterol
 
Blood glucose
 
 
 
	
 
Posttreatment: 
 
AG
 
UAG
 
AG/UAG
 
Body weight
 
Percentage fat mass
 
Body mass index
 
Waist circumference
 
Low-density lipoproteins
 
Total cholesterol
 
Blood glucose
 
 
 

### 1.3. Determination of Sample Size

Approximately 34 patients were planned to be randomized to 1 of 2 treatment sequences (GLWL-01/placebo or placebo/GLWL-01) in a 1:1 ratio. Thirty-four patients would provide approximately 80% power to detect an effect size of 0.75 for the HQ-CT total score using a 2-sided exact paired t-test with an  $\alpha=0.05$ , assuming 10% drop out.

## 2. GENERAL STATISTICAL METHODOLOGY AND CONVENTIONS

Chorus has designated EMB Statistical Solutions to generate the statistical analyses detailed in this SAP. All computations for statistical analyses will be performed using SAS® software, Version 9.4 or later. All SAS programs used in the production of statistical summary outputs will be validated with independent programming prior to finalization. In addition, all program outputs will be independently reviewed. The validation process will be used to confirm that all data

manipulations and calculations were accurately done. Once validation is complete, a senior statistical reviewer will perform a final review of the documents to ensure the accuracy and consistency with this plan and consistency within tables. Upon completion of validation and quality review procedures, all documentation will be collected and filed by the project statistician or designee.

Before implementation of parametric methods of analysis, the distribution of analysis variables will be examined to determine if model assumptions are satisfied. Transformations or nonparametric methods of analysis may be used if warranted. However, in some cases, nonparametric analysis may be the initially proposed method due to the expected distribution of response. Whenever alternative methods of analysis are required, the description of the new method along with the rationale for its use will be documented in the CSR.

The eCRF data for all patients will be provided in Standard Data Tabulation Model (SDTM) datasets. Any additional data listings supplied as part of the CSR will be sorted by investigative site and patient identification number, and patients will be identified in the listings by the investigator number concatenated with the patient number.

## **2.1. Randomization Schedule and Unblinding Plan**

This is a double-blind, 2-period, crossover study in which the patients, caregivers, investigators, and study site personnel will be blinded to treatment allocation. ClinPhone will be responsible for building the interactive response technology (IRT) system that randomly assigns treatment sequences (either Placebo/GLWL or GLWL/Placebo) to patients.

To preserve the blinding of the study, only a minimum number of Chorus personnel will see the randomization table and treatment assignments before the study is complete. This limited group will have access to unblinded treatment information to ensure the safety of patients in the study and to manage clinical trial supplies for the investigative sites. Site personnel and patients will remain blinded until the study is complete.

Emergency unblinding of site personnel may be performed through the IRT system. This option may be used ONLY if the patient's well-being requires knowledge of the patient's treatment assignment. All calls resulting in an unblinding event are recorded and reported by the IRT system.

Unblinding will occur after the last patient completes the study and all data management activities have been completed (i.e. data entered, coding completed, and all queries resolved).

## **2.2. Analysis Populations**

The **Entered Population** is defined as all patients who signed informed consent. The **Evaluable Population** is defined as all randomized patients who received at least one dose of double-blind study drug.

The Entered Population will be used to summarize enrollment at the study sites, for the summary of patient disposition, and in all listings. Otherwise, tables and figures will summarize the Evaluable Population according to the treatment the patient actually received. Any discrepancies between the randomized treatment and the treatment actually received will be noted in the listings.

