10.2. Populations for Analyses

For purposes of analysis, the following populations are defined:

Analysis Set	Description
Entered	All patients who sign informed consent
Randomized	All randomized patients who take at least 1 dose of double-blind study drug. Patients will be analyzed according to the treatment they actually received.

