10.3. Statistical Analyses

10.3.1. General Statistical Considerations

Statistical analysis of this study will be the responsibility of GLWL Research Inc. or its designee.

Efficacy analyses will be conducted on the randomized analysis set. This set includes all data from all randomized patients receiving at least 1 dose of double-blind study drug. Patients will be included in the analysis if they have a postbaseline measurement for the parameter being analyzed. Safety analyses will be conducted on the randomized analysis set. Patients will be analyzed according to the study drug they actually received.

Data will be presented using summary tables by treatment, unless otherwise specified.

Continuous data will be summarized using the mean, standard deviation, median (for selected variables), minimum, and maximum. Categorical data will be summarized as frequency counts and percentages. Figures may be used to support the presentation of selected data.

All tests of treatment effects will be conducted at a 2-sided alpha level of 0.05, unless otherwise stated.

Baseline values will be defined as the last available value prior to receiving double-blind study drug for each double-blind treatment phase.

For the purposes of follow-up analyses, the first 2 weeks of the washout period will be the follow-up for the Treatment Period 1 double-blind treatment phase and the Follow-up Period will be the follow-up for the Treatment Period 2 double-blind treatment phase.

Details related to handling of missing data will be described in the statistical analysis plan (SAP).

Any change to the data analysis methods described in the protocol will require an amendment only if it changes a principal feature of the protocol. Any other change to the data analysis

methods described in the protocol, and the justification for making the change, will be described in the SAP and/or in the clinical study report (CSR).

Additional exploratory analyses of the data will be conducted as deemed appropriate.

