## **2.9. Changes to the Planned Analyses**

Note that what is now called the **Evaluable Population** was called the **Randomized Population** in the protocol.

Blood glucose was added to the list of exploratory endpoints.

The determination of a treatment-emergent adverse event has been changed from that in the protocol, because the way adverse events are actually being captured is not as was anticipated. Specifically, an ongoing adverse event that worsens during the study will be captured as a new adverse event, so that adverse events that start during one period of the trial and get worse during a different period of the trial (which defines treatment-emergent) will have separate records that will be summarized separately.

The statistical analyses will be performed as 1-sided tests rather than 2-sided tests as originally planned, because enrollment was stopped prior to obtaining the intended 34 patients. With the anticipated 19 patients, there is at least 70% power for the primary treatment comparison, which is still considered acceptable for a proof of concept trial.

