## **6. EFFICACY ANALYSES**

Efficacy analyses for this study will be based on the findings from two instruments. First, the HQ-CT is a validated tool developed specifically for PWS to capture observations of problematic behaviors related to food. It consists of 9 items, with a 2-week recall period. The scale provides a composite value from 9 questions, each rated on a scale of 0 to 4 units (total range of score of 0 to 36; Fehnel et al. 2015).

Second, the CGIC is a single-item question rated on a 0 to 7 scale directed at the caregiver asking for an assessment of the overall improvement of patients with PWS.

Both of these assessments will be collected longitudinally during the study.

All efficacy analyses will be performed using the Evaluable Population. The method of analysis or statistical technique employed to address missing data will be described separately for each variable. Presentations of efficacy will include the number of patients with data at each time point plus related statistics derived from the analysis.

All statistical tests will be 1-sided.

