## **6.1. Primary Efficacy Analysis**

The primary efficacy analysis will examine the contrast between GLWL-01 and placebo for the post-treatment HQ-CT total score at the end of the double-blind treatment phase.

The primary analysis will be conducted using a restricted maximum likelihood-based, mixed-effect model repeated measures analysis. The model for the primary analysis will include the fixed, categorical effects of sequence, period, and treatment, as well as the continuous, fixed covariate of the baseline Treatment Phase 1 HQ-CT score minus the baseline Treatment Phase 2 HQ-CT score (diff) and the interaction of period-by-diff (Mehrotra, 2014).

An unstructured covariance matrix will be used to model the within-patient errors.

Satterthwaite's approximation will be used to estimate the denominator degrees of freedom. The significance of differences in least-square means will be based on Type III tests using the observed population margins. The analyses will be performed using the SAS procedure PROC MIXED.

The tabular output for these MMRM analyses will present the least squares means, standard errors, and 95% confidence intervals for each marginal main effect. Pairwise contrasts of the least squares means between GLWL-01 and Placebo will also be provided at each time point using LSMESTIMATE statements.

Descriptive statistics for the HQ-CT score and the within-treatment phase changes from baseline will be provided by treatment and time point.

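### Primary efficacy is grouped by treatment received, no as-randomised analysis is planned, and the basis of the model's sequence term is not stated

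*SAP*

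**What the plan says.** Protocol 10.2 defines a Randomized set of randomised patients with at least one double-blind dose, and adds: "Patients will be analyzed according to the treatment they actually received". Protocol 10.3.1 then states: "Efficacy analyses will be conducted on the randomized analysis set".

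The SAP carries this over. SAP 2.2 defines the Evaluable Population as "all randomized patients who received at least one dose of double-blind study drug", and SAP 2.9 notes that this set "was called the Randomized Population in the protocol". SAP 2.2 exempts only enrolment, disposition and listings from the rule that "tables and figures will summarize the Evaluable Population according to the treatment the patient actually received". For mismatches it says: "Any discrepancies between the randomized treatment and the treatment actually received will be noted in the listings". SAP 6 states: "All efficacy analyses will be performed using the Evaluable Population".

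SAP 6.1 makes no exception for the primary analysis. Its model contains "fixed, categorical effects of sequence, period, and treatment", together with the baseline difference and its interaction with period. It does not say whether sequence is as randomised or as received. SAP 6.1.1 makes sensitivity analyses optional, leaves their content to an addendum, and ties them to a positive primary result.

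**The concern.** Grouping by treatment received is normal for safety. For efficacy, the usual choice is the allocation made at randomisation, because nothing that happens afterwards can change it. Here one as-received rule covers both, and no as-randomised analysis stands behind it, even as support.

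Two things are at stake if a patient is given the wrong treatment in a period. First, the primary contrast then uses a grouping formed partly after randomisation. Second, the model needs a decision that the SAP does not make: which sequence such a patient belongs to. With enrolment down from 34 to an anticipated 19, each patient carries more weight. Finding a mismatch means comparing assigned with received treatment, which is unblinded information, so the rule should be settled before unblinding.

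**Working it through.** **Inputs.** From Protocol 10.1 and SAP 1.3: 34 patients, effect size 0.75, two-sided paired t-test at 0.05, about 80% power, 10% dropout. From SAP 2.9 and SAP 6: 19 anticipated patients, one-sided tests, at least 70% power. The SAP gives no level for the one-sided test, so 0.05 is assumed. Neither document gives a dispensing-error rate, so m = 0 to 3 patients with the two treatments reversed is assumed.

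**1. The plan's own figures.** 30/0.9 = 33.3, rounded up to 34, so about 30 completers are expected. The documents do not define the SD behind the 0.75.
- If it is the SD of the paired differences, noncentral-t power at 30 is 97.8%, which does not match.
- If it is the single-period SD with zero within-patient correlation, the standardised paired effect is 0.75/√2 = 0.530. Power at 30 is then 80.2%, which matches. At 19, one-sided 0.05, it is 71.9%, which matches the SAP's statement.

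Neither figure depends on the grouping rule. Changing the rule alters no stated sample size or power.

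**2. Where the groupings differ.** Take a patient randomised to GLWL-01/placebo, with treatment coded as received:

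| Received in periods 1/2 | Sequence coded as randomised | Sequence coded as received |
|---|---|---|
| GLWL-01/placebo | codes agree | codes agree |
| placebo/GLWL-01 | treatment contradicts sequence in both periods | codes agree, but sequence is now a post-randomisation grouping |
| same treatment twice | treatment contradicts sequence in one period | neither of the two sequences applies |

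Only the last two rows differ from an as-randomised analysis, and each needs a dispensing or supply error. With no error the two analyses are the same.

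**3. Effect on the error rate.** A 2×2 crossover with no treatment effect was simulated (n = 19, one-sided 0.05, 5,000 runs), using the two-sample t-test on period differences. The simulation standard error at 5% is √(0.05 × 0.95/5000) = 0.3 percentage points.

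| Reversals | Which patients | As received | As randomised |
|---|---|---|---|
| 1 | unrelated to outcome | 5.1% | 5.1% |
| 2 | unrelated to outcome | 4.7% | 4.3% |
| 1 | extreme case | 17.7% | 4.9% |
| 2 | extreme case | 42.4% | 4.6% |

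In the extreme case the errors are made to fall on exactly the patients whose regrouping most favours the drug. It bounds what could happen and is not a forecast.

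**4. Price of the as-randomised analysis.** A reversed patient contributes the effect with the wrong sign, so the expected effect is multiplied by 1 − 2m/n. With n = 19, the SD of differences held fixed, and the effect scaled as in step 1:

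| m | 1 − 2m/19 | Effect size | Approximate one-sided power |
|---|---|---|---|
| 0 | 1.000 | 0.75 | 0.719 |
| 1 | 0.895 | 0.67 | 0.635 |
| 2 | 0.789 | 0.59 | 0.544 |
| 3 | 0.684 | 0.51 | 0.451 |

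A patient given the same treatment twice contributes zero, so the factor is 1 − m/n. For one such patient, 18/19 = 0.947 and 0.75 × 0.947 = 0.71.

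**The case against.** A reader might infer that the plan gives up the protection of randomisation for its primary comparison. The documents do not support that. The set holds only randomised, dosed patients. Bottles are assigned through the interactive web-response system (Protocol 7.2), patient, caregiver and investigator are blinded in the double-blind phases (Protocol 7.3), and active and placebo capsules look identical (Protocol 7.1). Nobody in the trial chooses the treatment, so the usual route to as-treated bias is largely closed. What remains is dispensing or supply error under blind, with no evident link to outcome, and step 3 shows an error rate near 5% in that case. This objection stands.

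One patient of 19 is 5.3% of the sample, against 2.9% of 34. A reader might take the 5.3% as the size of a bias. It is only that patient's share of the data.

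The code conflict also should not be overstated. It depends on sequence being coded as randomised, which SAP 6.1 leaves open. Even then the model does not fail, because the other patients still estimate the treatment effect.

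In a proof-of-concept trial, estimating the effect of the drug actually taken is a defensible aim, and as-randomised grouping costs power when errors occur (step 4). Mismatches are also listed under SAP 2.2, and dispensing errors plausibly fall under the deviations that SAP 3.1 has blinded staff identify.

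These points limit the severity. They do not supply an as-randomised analysis or define the sequence term.

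**Conclusion.** The point holds as a conditional weakness in a stated rule. Both documents group the primary and other efficacy analyses by treatment received, none is planned as randomised, and the basis of the sequence term is left open. If a patient is mis-dispensed, the primary estimate is not strictly a randomised comparison and its codes may conflict.

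The size is nil if no error occurs, and the documents report none. One or two reversals unrelated to outcome leave the one-sided error rate at 19 patients near 5%. The 17.7% and 42.4% figures need errors aligned with outcome in the worst possible way, and nothing in the documents suggests that. The change is worth making because it is cheap, follows usual practice for efficacy, and settles beforehand a coding decision that would otherwise fall to the programmer.

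The conclusion about wording rests on the text alone. The numbers rest on the assumed one-sided 0.05 level, the assumed count of reversals, and, for power, the reading of 0.75 that reproduces the plan's figures.

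**What to change.** Before unblinding:

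- In SAP 2.2 and 6, state that the primary and secondary efficacy models use the randomised sequence and the treatment assigned to each period. Repeat this for the sequence and treatment terms in SAP 6.1.
- If any discrepancy occurs, add an as-received analysis as support, and say how a patient given the same treatment twice enters it.
- Keep treatment received for safety, pharmacokinetics and the AG/UAG measures, where it is the natural grouping. SAP 8 borrows the primary method for all exploratory endpoints, so it needs a line saying this, and naming the grouping for the anthropometric and blood-chemistry endpoints.
- Keep the listing of discrepancies.
- Record the departure from Protocol 10.2, with its justification, in SAP 2.9. Protocol 10.3.1 requires an amendment only if a principal feature changes, and the sponsor should document its judgement on that.

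The cost is a few sentences of SAP text, with no change to sample size or data collection. The statistical cost arises only if errors occur: with one reversed patient of 19, the as-randomised effect falls from 0.75 to about 0.67 and approximate one-sided power from about 72% to about 63%. The supportive as-received analysis would show how much of a weaker result comes from that dilution.
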